Study Title: Comparative Tests of Flu Vaccination Phone Messages

Summary of Research Protocol

October 30, 2017

This project is an unfunded research collaboration between Emmi Solutions, Inc., and a team of academic research investigators led by [name]. of the University of Michigan.

Emmi Solutions provides services that educate, support, remind, and ultimately prompt people to take actions toward better health on behalf of various clients, which include individual physicians or medical practices, hospital systems, and health insurance companies. As part of their service to their clients, Emmi deploys outbound, automated, Interactive Voice Response phone calls with the outlined variations to patients identified by Emmi's clients as eligible for the flu vaccine.

This study will begin by gaining consent from specific clients of Emmi Solutions to share de-identified data collected on their patient populations with the investigators for the purpose of investigating the effectiveness of different telephone scripts at promoting behavioral intentions related to vaccination.

Calls will be made at times and at a rate specified by Emmi's clients using Emmi's in-house automatic deployment system. Pre-recorded messages that adjust to patient responses will follow interaction outlines, or "scripts" developed by Emmi for the purpose of encouraging uptake of seasonal influenza vaccination. Contact information and basic demographic information about each patient is provided by the client based on their own processes and is confidentially maintained by Emmi as part of their services.

Within each client's list of patients, Emmi will randomly assign patients to receive different versions of the flu call script. Patients of larger clients will be randomized among the full set of experimental arms, while patients of smaller clients may be randomized among a smaller subset of arms to ensure statistical power for comparisons within each client's patient set, with the decision to be based on the size of the provided patient list.

As part of Emmi's standard process, each call includes one or more questions that recipients can answer during the call (e.g., by saying "yes" to the question). For the calls included in this study, at least one question will measure patients' behavioral intentions to receive an influenza vaccine.

Emmi's database records each patient's responses over the course of the call and generates one report of all patients' responses for Emmi's clients to review. This report includes Protected Health Information, such as patient names and phone numbers.

As part of this research, however, Emmi will then de-identify the reports to meet the standards of the Health Insurance Portability and Accountability Act and then send the de-identified response reports, as well as linked demographic information and call timing data, and send them to the investigators via Secure File Transfer Protocol, the preferred trusted protocol used between Emmi and their clients. Each patient record will not include any Protected Health Information and will be identified only by a unique identification number. Only Emmi will maintain and have access to the mapping algorithm that could enable matching of individual records to contact information or other protected health information.

Certain clients of Emmi also have access to other information about their patients, such as data that may indicate whether a patient actually obtains an influenza vaccination during the 2017-2018 influenza season. If clients share these data with Emmi, Emmi will in turn share with investigators (again, only using the unique patient id number and secure file transfer) for inclusion of these variables in analyses.

The research investigators (led by [name]) will then conduct statistical analyses to determine if the rates of behavioral intentions to vaccinate (and actual vaccination status, when available) differed among the study arms. After preliminary bivariate analyses (e.g., chi-squared analyses), logistic regression analyses will control for variation among clients (both because client populations vary in unmeasured ways and because call timing will be different for different clients) and include available demographic information when possible.

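### Does cutting arms at smaller clients by list size, with no power inputs stated and no within-client comparison in the analysis paragraph, call for a change?

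*Combined protocol and SAP*

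**What the plan says.** The document is a short summary without numbered sections. Three of its paragraphs bear on this point.

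- **Random assignment.** Patients are randomised inside each client's list. "Patients of larger clients will be randomized among the full set of experimental arms"; smaller clients may use a subset "to ensure statistical power for comparisons within each client's patient set", "with the decision to be based on the size of the provided patient list". The wording for smaller clients is permissive, and no list size is given as a threshold.
- **Call questions.** "each call includes one or more questions that recipients can answer during the call", and for the study calls "at least one question will measure patients' behavioral intentions to receive an influenza vaccine". No expected answer rate is given.
- **Analysis.** The question is whether rates of intention, and of vaccination where known, "differed among the study arms". Bivariate tests come first, with chi-squared as the example; then "logistic regression analyses will control for variation among clients". No per-client result or client-by-arm term is named. Vaccination status depends on the client: "If clients share these data with Emmi, Emmi will in turn share with investigators".

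**The concern.** Two things look wrong.

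First, the rule uses list size, but a stated intention can be recorded only for a patient who answers the question. The information on intention is therefore governed by list size times an answer rate that the document does not give. The same list could support many arms or hardly any.

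Second, arms are cut to protect comparisons within a client, while the analysis paragraph treats client only as something to adjust for. If no within-client comparison is made, the pooled analysis loses information on the dropped arms and nothing named in the plan gains.

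The timing adds weight. Once a list has been randomised and called, no analysis can recover an arm that its patients never received.

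**Working it through.** **Inputs.** The document states no sample size, power, alpha, rate, difference, arm count or answer rate, so there is no figure of its own to reproduce. All inputs below are assumptions: intention 50% against 55%, two-sided 5%, equal arms, pairwise tests without multiplicity correction, and only answering patients counted.

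**Formulas.** With d = p2 − p1 and m = (p1 + p2)/2:

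- n per arm = [z(α/2)·√(2m(1−m)) + z(power)·√(p1(1−p1) + p2(1−p2))]² / d²
- power = Φ{[d√n − z(α/2)·√(2m(1−m))] / √(p1(1−p1) + p2(1−p2))}

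For 80% power: (1.960 × 0.7062 + 0.8416 × 0.7053)² / 0.05² = 1,564.7, so 1,565 answers per arm.

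**1. Does list size alone fix power?** Take a list of 20,000.

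| Answer rate | 4 arms: n per arm, power | 6 arms: n per arm, power | Arms supported at 80% power (20,000 × rate / 1,565) |
|---|---|---|---|
| 50% | 2,500, 94% | 1,667, 82% | 6.39 |
| 25% | 1,250, 71% | 833, 53% | 3.19 |
| 10% | 500, 35% | 333, 25% | 1.28 |

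It does not. But for 50% against 60% over 4 arms, the same list gives power of about 89% even at 10% answering, and more at the higher rates. The rule can succeed or fail, and the document does not settle which.

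**2. What does cutting arms do to the pooled, client-adjusted comparison?** Take six smaller clients, each with 4,000 listed and 25% answering: 1,000 answers each, 6,000 in all.

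- *Full set of 4 arms.* 6,000/4 = 1,500 per arm; pooled pairwise power 78%. Within one client: 250 per arm, 20%.
- *Two arms each, all six pairs used once.* With client effects in the model, efficiency is v(k−1)/[k(v−1)] = 4 × 1/(2 × 3) = 2/3. The effective number is 1,500 × 2/3 = 1,000 per arm; pooled power 61%. Within one client: 500 per arm, 35%.
- *The same two arms at all six.* 6 × 500 = 3,000 per arm; pooled power for that contrast 97%. These clients then give nothing on the other two arms.

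**3. Add one larger client with the full set:** 20,000 listed, 25% answering, 1,250 per arm.

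- *No cut:* 1,500 + 1,250 = 2,750 per arm, 96%.
- *Balanced pairs:* effective 1,000 + 1,250 = 2,250 per arm, 92%.
- *Common pair:* the retained contrast has 3,000 + 1,250 = 4,250 per arm, above 99%. The contrast between the two dropped arms rests on the larger client's 1,250 per arm, 71%.

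So the sign and size of the effect depend on which arms are kept and on how much full-set data the larger clients bring. The document fixes neither.

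**4. Validity.** Arms are randomised inside each list and the regression adjusts for client, so each arm contrast is built from comparisons between patients of the same client. Unequal arm sets do not bias those contrasts once client is in the model.

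**The case for a change.** The strongest case for a change is that this is the only plan available and that the decision cannot be undone after the calls. A few sentences before randomisation would state the cut-off as expected answers per arm, say whether per-client results will be reported, and either keep the full arm set at smaller clients or balance the subsets. In the six-client example, the balanced cut lifts within-client power only from 20% to 35%, so even the stated aim is missed. The choice of arms also matters: if three clients kept arms 1 and 2 and three kept arms 3 and 4, the contrast of arm 1 with arm 3 could not be estimated from those clients at all.

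The facts behind this stand, but they do not carry a change.

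- An unstated cut-off is not a wrong one. Those who set it may already allow for non-answer, and for vaccination status, where shared, listed patients can be the denominator.
- The bivariate analyses are open-ended and could be run by client. The random assignment paragraph names within-client comparisons as an aim, so the analysis paragraph is silent on a reporting level rather than in contradiction.
- The estimability problem needs an awkward split of arms and no full-set client. Under the plan, larger clients carry every arm and link the contrasts.
- Keeping the full set everywhere would override a stated design aim. Balancing subsets would give up the chance to concentrate power on a priority contrast.
- A threshold of 1,565 answers per arm would not be neutral either. With four arms there are six pairs, and a Bonferroni level of 0.05/6 raises it to about 2,415.

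**Conclusion.** No change to the plan follows. The missing cut-off, answer rate and reporting level are details that the team can settle sensibly when each list arrives, with valid results either way. The number of arms at smaller clients is a fair trade-off: fewer arms lose information on those dropped and gain it on those kept in common.

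The loss from 78% to 61% is not a general cost. It belongs to one layout, balanced pairs, over the cut clients alone. It shrinks to 96% against 92% with one assumed full-set client, and becomes a gain to 97% for the retained contrast under a common pair. All these figures rest on the assumed rates, list sizes, answer rates and arm counts, and on uncorrected pairwise tests. The conclusion that only precision is at stake rests on randomisation within each list and on the adjustment for client, both of which the document states.

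When the results are written up, readers will want to know which arms each client used, how the subsets were chosen, and whether single-client results are exploratory.

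### Does leaving the denominator of the intention rate unstated call for a change to the plan?

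*Combined protocol and SAP*

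**What the plan says.** All of this is in the Combined protocol and SAP, under Summary of Research Protocol.

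- **Aim.** The study is for "investigating the effectiveness of different telephone scripts at promoting behavioral intentions related to vaccination".
- **Randomisation.** The call company assigns individual patients on each client's list to a script. The assignment does not depend on the call being answered.
- **Outcome.** Intention comes from the call itself: "each call includes one or more questions that recipients can answer during the call", and "at least one question will measure patients' behavioral intentions to receive an influenza vaccine". The scripts branch: "Pre-recorded messages that adjust to patient responses will follow interaction outlines".
- **Analysis.** The final paragraph says the investigators will "determine if the rates of behavioral intentions to vaccinate (and actual vaccination status, when available) differed among the study arms". They begin with simple tests such as chi-squared, after which "logistic regression analyses will control for variation among clients", with demographics added where available.
- **Data.** "Each patient record will not include any Protected Health Information and will be identified only by a unique identification number". The call company keeps the key.
- **Second outcome.** Actual vaccination is added where clients can supply it: "Certain clients of Emmi also have access to other information about their patients".

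The documents do not name the denominator of the intention rate or the coding of patients who give no answer. They also give no significance level, number of arms, sample size, or expected reach, answer or intention rate.

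**The concern.** A rate needs a denominator, and an automated call will foreseeably miss some patients, lose others and meet silence from more. At least two readings fit the text: recorded yes over all randomised patients, with everyone else counted as not yes, and yes over those who answered. A third, yes over those reached, is possible if pick-up is logged and transferred, which the documents do not promise.

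Two things seem to be at stake.

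1. **False positives.** If the denominator is settled only after the results are known, a script could be declared better on whichever version crosses 5%. Adjusting for client does not prevent this, because adjustment does not decide who enters the model.
2. **Bias.** If only answerers are compared, and one script drives away more reluctant listeners before the question, the compared groups are no longer those that randomisation formed. Branching scripts make that conceivable.

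**Working it through.** **Inputs.** The plan has no figure to reproduce. Everything numerical here is assumed: two-sided 5% level; reached q = 0.3, 0.5 or 0.7; answering among reached a = 0.4, 0.6 or 0.8; yes among answerers p = 0.3, 0.5 or 0.7. The middle case is q = 0.5, a = 0.6, p = 0.5.

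**1. False positives with identical scripts.** Write π = q·a·p for the share of randomised patients with a recorded yes. In large samples the test statistics for the all-randomised and answerers-only comparisons are jointly normal with correlation √((1−p)/(1−π)), whatever the sample size.

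| q, a, p | π | Correlation | At least one test significant |
|---|---|---|---|
| 0.7, 0.8, 0.3 (lowest) | 0.168 | √(0.7/0.832) = 0.917 | 6.9% |
| 0.5, 0.6, 0.5 (middle) | 0.150 | √(0.5/0.85) = 0.767 | 8.0% |
| 0.3, 0.4, 0.7 (highest) | 0.084 | √(0.3/0.916) = 0.572 | 8.9% |

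The excess over 5% is therefore 1.9 to 3.9 percentage points. With the reached-only test as a third option, the range is 7.5% to 10.7%. Binomial simulation of the middle case with all three gives about 9%, and about 5% for each test alone. Client-adjusted logistic regression in three simulated four-client settings gives 8.2%, 9.0% and 10.6% for any of three, against 4.6-5.3% for any single one. So the excess comes from choosing late, not from any one denominator.

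**2. Do the two readings contradict each other?** With identical scripts in the middle case (4,000 per arm), the two estimates have opposite signs in about 22% of trials. Opposite signs with either test significant occur in only about 0.04%. Nearly all the sign differences are noise around zero.

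**3. With a true difference.** Take 55% against 50% yes among answerers, equal reach and answering, 4,000 per arm.

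- All randomised: yes shares 0.5·0.6·0.55 = 0.165 and 0.5·0.6·0.50 = 0.150. z = 0.015/√(2·0.1575·0.8425/4,000) = 1.84; power = Φ(1.84 − 1.96) = 45%.
- Answerers: 4,000·0.5·0.6 = 1,200 per arm. z = 0.05/√(2·0.525·0.475/1,200) = 2.45; power = Φ(2.45 − 1.96) = 69%.

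The two disagree on significance in about 30% of simulated trials. In about 27 of those 30 points only the answerers test is significant, as its greater power implies; about 3 go the other way. None were significant in opposite directions.

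**4. If answering itself differs by script.** Take 50% reached and 2,000 per arm.

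- Answering 50% against 55%, yes among answerers 50% in both arms: the recorded-yes shares are 0.125 and 0.1375. The all-randomised test rejects in 21% of trials, the answerers test in 5%.
- Answering 50% against 55%, yes among answerers 55% against 50%: recorded-yes shares are 0.1375 in both arms. The all-randomised test rejects in 5%, the answerers test in 37%.

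The readings answer different questions, and neither is right in every case. The documents do not say where the intention question sits or where the scripts diverge, so they do not show that answering would differ. Branching on a patient's replies is not evidence that one script loses more listeners than another.

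**The case for a change.** The strongest case for a change is that this text is the whole plan. It already names tests and covariates, and one more sentence would fix the denominator at almost no cost. The description of a report covering all patients' responses does not settle the matter, because it describes what clients receive, not an analysis set. If the transferred file held only responders, the investigators could not compute the all-randomised rate or the answer rate by arm from it.

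Most of this stands as description. The denominator is unstated, the readings are different tests, and writing the choice down would be good practice. It falls short of showing a fault in the plan, for four reasons.

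- The plan states no wrong rule. The inflation needs a choice made after the results are seen, which the documents do not suggest.
- The remedy is to state a choice that can legitimately go either way. It adds detail rather than correcting anything.
- The text does not say that non-responders are left out of the transfer. The call company does the randomising and keeps the identifiers, so it is placed to supply counts by arm on request.
- Naming a denominator would not by itself control the error rate. The level, the number of arms and any multiplicity rule are also unstated, and a call may carry more than one intention question.

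Vaccination status, where supplied, does not depend on answering and is free of the difficulty.

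**Conclusion.** No change follows. The omission is a gap that analysts would ordinarily fill by choosing a denominator and reporting it, and the choice is a fair trade-off between keeping the randomised comparison and measuring intention with more power. Any single choice made beforehand holds about 5% when scripts are identical. The worst the gap permits, if the choice between all randomised and answerers were made on the results, is 6.9-8.9% per comparison, or up to 10.7% if pick-up data allowed a third version. Those figures rest wholly on assumed reach, answer and intention rates and an assumed 5% level. Bias from unequal answering cannot be estimated from the documents, which do not show that it would occur. A reader of the results should check which denominator was used and what share answered in each arm.

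### Does the plan need to fix the intention question, the script contrasts and alpha before claims about individual scripts can be trusted?

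*Combined protocol and SAP*

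**What the plan says.** The document is a short summary without numbered sections. Four of its paragraphs bear on this point.

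- **Purpose.** The study is to look at the "effectiveness of different telephone scripts at promoting behavioral intentions related to vaccination". Vaccination itself is not part of this statement of purpose.
- **Randomisation.** Large client lists use every script: "Patients of larger clients will be randomized among the full set of experimental arms". Short lists can be treated differently, in that "patients of smaller clients may be randomized among a smaller subset of arms". The reason given for the smaller subsets is power for comparisons inside each client's list. Neither the number of arms nor a reference script is given.
- **Call questions.** "at least one question will measure patients' behavioral intentions to receive an influenza vaccine". One question satisfies this wording, and so do several.
- **Analysis.** The investigators are to "determine if the rates of behavioral intentions to vaccinate (and actual vaccination status, when available) differed among the study arms". Chi-squared tests are described as preliminary; after them, "logistic regression analyses will control for variation among clients", with demographics added where possible.

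No alpha, sidedness, multiplicity rule or list of contrasts appears anywhere, and no redaction mark suggests that one was removed.

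**The concern.** The purpose is to learn how different scripts perform, and readers will want to know which one did better. A significant overall test does not tell them. To name a script, the analyst must choose an intention question, a set of contrasts and a significance level, and the plan leaves all three open. A full set and a smaller subset that is itself randomised imply at least three arms, so there are at least three possible pairs. Vaccination status may add a second outcome, and within-client comparisons may add more tests. If each were tested at 5% and the best result picked out, a script could be called better by chance alone, and nothing in the plan says how often that would happen.

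**Working it through.** The plan states no error rate, power or sample size, so there is no figure of its own to reproduce. The check asks how large the problem could be, whether the stated question suffers from it, and what a strict remedy would cost.

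**Inputs.** From the document: more than two arms, a comparison among arms, and client-adjusted logistic regression. Assumed: two-sided 5% per test, 3 to 6 arms of equal size, and normal approximations.

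**1. The stated question.** One overall test with K − 1 degrees of freedom on one intention question has a 5% error rate for any number of arms. In a simulated unequal case (half the patients in clients using only two arms, client effect removed) the rate was also 0.050.

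**2. Unadjusted script contrasts, all scripts equal.** There are K(K − 1)/2 pairs, or K − 1 contrasts with a reference. If m tests were independent, the chance of a false finding would be 1 − 0.95^m. Contrasts that share an arm are correlated, so the exact values, by numerical integration at |z| > 1.96, are lower.

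| Arms | Pairs m | 1 − 0.95^m | Exact | Reference m | 1 − 0.95^m | Exact |
|---|---|---|---|---|---|---|
| 3 | 3 | 0.143 | 0.122 | 2 | 0.098 | 0.091 |
| 4 | 6 | 0.265 | 0.203 | 3 | 0.143 | 0.125 |
| 5 | 10 | 0.401 | 0.286 | 4 | 0.185 | 0.156 |
| 6 | 15 | 0.537 | 0.366 | 5 | 0.226 | 0.183 |

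**3. More than one outcome or question.** Two independent overall tests give 1 − 0.95² = 0.098, and three give 1 − 0.95³ = 0.143. At a correlation of 0.7 the simulated values are about 0.08 and 0.11. Exactly one intention question is consistent with the plan; in that case only vaccination adds an overall test.

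**4. Overall test first, then unadjusted pairs.** If one script differs strongly, the overall test is almost always significant and the other K − 1 equal scripts are compared freely. The false-claim rate is then the all-pairs rate for K − 1 arms. For 3, 4, 5 and 6 arms this is 0.050, 0.122, 0.203 and 0.286. An overall gate alone is therefore enough with three arms but not with more.

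**5. The cost of strict control.** One rule that holds 5% is the overall test followed by Holm, with the divisor capped at the most contrasts that can still be null: (K − 1)(K − 2)/2 = 1, 3, 6, 10 for all pairs, or K − 2 = 1, 2, 3, 4 against a reference. A contrast with 80% unadjusted power has an expected z of 1.960 + 0.842 = 2.802. As a rough guide, its power at 0.05/c is Φ(2.802 − z), where z is the two-sided critical value at 0.05/c:

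- c = 3: Φ(2.802 − 2.394) = 0.66
- c = 6: Φ(2.802 − 2.638) = 0.57
- c = 10: Φ(2.802 − 2.807) = 0.50

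The overall gate lowers these values and Holm's later steps can raise them. Simulated ranges for the full rule, across the patterns of script effects tried, are:

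| Arms | All pairs | Against a reference |
|---|---|---|
| 3 | 70–76% | 70–80% |
| 4 | 60–66% | 62–72% |
| 5 | 52–57% | 55–69% |
| 6 | 45–50% | 51–66% |

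The low end arises when two scripts deviate in opposite directions, which for reference contrasts means the reference and one other script.

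**The case for a change.** The strongest case for a change is that the omissions are plain, the purpose concerns scripts rather than a global difference, and a few sentences written before analysis would close the gap at no cost to calls, randomisation or the overall test. Step 4 supports this: with four or more arms, a significant overall test followed by free pairwise testing does not protect statements about individual scripts.

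The omissions and the arithmetic stand. Three things limit what follows from them.

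- The analysis paragraph frames its question as a difference among arms, which a single test answers. It already marks chi-squared as preliminary and puts vaccination in parentheses, and the purpose is stated wholly in terms of intentions. An informal order of outcomes can be read from the text.
- Adjusting across distinct scripts in a low-risk messaging study is a matter of judgement. Even someone who wants the gap closed would have to accept unadjusted contrasts labelled exploratory as an adequate answer. What is left is wording.
- A strict hierarchy headed by the pooled test would reduce the within-client comparisons to description. Those are the only comparisons for which the document mentions power, so the remedy has a further cost.

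**Conclusion.** No change to the plan is needed. The gap is real, but it consists of routine detail and a fair trade-off. One client-adjusted overall test on one intention question answers the stated question at 5%, taking the usual level as given. Analysts can be expected to identify the question, report every arm's rate with its interval, treat vaccination as supporting evidence and present script contrasts as exploratory.

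The possible inflation is 9 to 18% against a reference and 12 to 37% over all pairs. Both ranges rest on an assumed 3 to 6 equal arms and unadjusted 5% tests, none of which the documents state. Strict control would bring such errors to 5% but would leave an 80%-power contrast with between 45 and 80%, depending on arms, contrasts and effects.

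The conclusion would weaken if a report presented one selected script contrast, or one selected question, as confirmed. That is a point for reading the results.

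### Does the preliminary chi-squared test confound client with script if smaller clients use fewer arms, with nothing said on which analysis decides?

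*Combined protocol and SAP*

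**What the plan says.** All the relevant text is in the Summary of Research Protocol, which has no numbered sections.

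The randomisation paragraph makes the client the stratum: "Within each client's list of patients, Emmi will randomly assign patients to receive different versions of the flu call script". The set of arms may depend on the client. For long lists the rule is: "Patients of larger clients will be randomized among the full set of experimental arms". Short lists can be handled differently, in that "patients of smaller clients may be randomized among a smaller subset of arms to ensure statistical power for comparisons within each client's patient set". List size settles which applies: "with the decision to be based on the size of the provided patient list". The number of arms, the size threshold and the identity of any subset are not given.

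The closing paragraph, on analysis, has two steps in order: "After preliminary bivariate analyses (e.g., chi-squared analyses), logistic regression analyses will control for variation among clients". Its reason for the adjustment is that "client populations vary in unmeasured ways and because call timing will be different for different clients". Demographic variables are added where they are available. It does not say whether the chi-squared tests are run within client or over all clients. It does not name a primary analysis, and it does not say what happens if the two steps disagree.

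**The concern.** Randomisation within client protects comparisons within client. It protects a comparison pooled over clients only if every client uses the same arms in the same proportions. If smaller clients keep only some arms, those arms hold a larger share of smaller-client patients than the arms used by larger clients alone. If intention rates also differ between the two kinds of client, a plain table of outcome by arm shows differences between scripts that do not exist.

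The plan permits the first condition and expects client populations to differ. A literal reading of a bivariate test is outcome by arm with no client term, so an analyst could run the pooled test without departing from the text. With no deciding analysis named, a significant crude difference could be reported beside a null adjusted result, or in place of it. Pooled crude rates could also rank scripts wrongly.

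**Working it through.** The documents give no client sizes, arm count, outcome rates or significance level, so there is no figure to reproduce. All inputs below are assumptions.

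**Set-up.** There is no script effect. There are four arms, A to D, with equal allocation. Larger clients use all four arms with intention 40%. Smaller clients use A and B only, with intention p. The test level is 5%.

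**Crude rates at 8,000 larger-client and 2,000 smaller-client patients.** A and B each hold 2,000 + 1,000 = 3,000 patients. C and D each hold 2,000.

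- Crude rate in A and B = (2,000 × 0.40 + 1,000 × p) / 3,000.
- p = 0.50 gives (800 + 500) / 3,000 = 43.3%, against 40.0% in C and D.
- p = 0.42, 0.45 and 0.60 give 40.7%, 41.7% and 46.7%.

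**Pooled chi-squared test, 3 degrees of freedom.** The noncentrality is Σ n(rate − mean)² / [mean(1 − mean)].

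- p = 0.50: the mean is 0.42. The numerator is 2 × 3,000 × 0.01333² + 2 × 2,000 × 0.02² = 1.067 + 1.600 = 2.667. Dividing by 0.42 × 0.58 = 0.2436 gives 10.95, so the test rejects about 80% of the time.
- p = 0.45: the mean is 0.41. The numerator is 2 × 3,000 × 0.00667² + 2 × 2,000 × 0.01² = 0.267 + 0.400 = 0.667. Dividing by 0.41 × 0.59 = 0.2419 gives 2.76, so the test rejects about 25% of the time.

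Rejection rates of the pooled test for other sizes, all with no script effect:

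| Larger / smaller patients | p = 42% | 45% | 50% | 60% |
|---|---|---|---|---|
| 8,000 / 2,000 | 8% | 25% | 80% | 100% |
| 2,000 / 500 | 6% | 9% | 24–25% | 80% |
| 8,000 / 800 | 6% | 9% | 23–24% | 76% |

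With p = 40%, so that clients do not differ, the rate is about 5%.

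**Client-adjusted analysis.** Twenty scenarios (four size pairs, five values of p) were simulated with 10,000 data sets each. The likelihood ratio test for arm in a logistic model with client main effects, and a Cochran-Mantel-Haenszel test stratified by client, rejected between 4.7% and 5.5% of the time throughout. A separate check with a 30% baseline and 4,000 / 1,000 patients gave 4.7% to 5.4% for the logistic model. In that check the pooled test rejected 15% to 99% of the time when smaller clients used two arms and their rate was 5 to 20 points higher.

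**Dependence on the assumed pattern.**

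- If smaller clients use three of the four arms at 8,000 / 2,000, the pooled test rejects about 12% (p = 45%) and 37% (p = 50%).
- If half the smaller-client patients are on A/B and half on C/D with like rates, each arm has (2,000 × 0.40 + 500 × 0.50) / 2,500 = 42.0%, and the bias is gone.
- If all clients use all arms in the same shares, the rate is about 5%.

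**Reading the two paragraphs together.** The chi-squared step is labelled preliminary. The regression follows it, and the reason given for the regression is the same client difference that would distort a pooled test. The reason given for using fewer arms is "to ensure statistical power for comparisons within each client's patient set", which points to within-client tests. Those do not have this problem.

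**The case for a change.** The strongest case for a change is that the wording permits the wrong test and never forbids its use. Client control is attached only to the regression. Calling a step preliminary suggests that it does not decide, but it does not say so, and it does not stop pooled rates and p-values from being tabulated as script comparisons. The sponsor's clients range from individual physicians to insurers, so large differences in intention are plausible. Two or three sentences would settle the matter, with no loss of precision in the main model.

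Much of this stands. The mechanism is real, the arithmetic reproduces, and no sentence names the deciding analysis. But the harm needs several things together: subsets are actually used, the chi-squared test is pooled, client rates differ materially and in line with the arms, and the crude result is then allowed to override the adjusted one. The last runs against the plan's own sequence and rationale. A stratified preliminary test would give the reader nothing material beyond the adjusted model already planned.

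A related worry is that the adjusted model borrows indirectly across clients when it compares arms that not all of them used. This misleads only if script effects differ by client. In a constructed example, smaller clients have A at 50% and B at 40% (1,000 each), and the larger client has 40% in every arm (2,000 each). The A versus C odds ratio is 1.07, with |z| about 1.1. Restricting that contrast to clients that used both arms is optional. With 8,000 / 2,000 patients it would raise the standard error of the log odds ratio from 0.0617 to √(2 / (2,000 × 0.4 × 0.6)) = 0.0645, about 5%.

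**Conclusion.** No change is needed. A pooled chi-squared test could mislead badly. Under the assumed 8,000 / 2,000 split its false-positive rate runs from about 8% for a 2-point client difference to about 80% for a 10-point one. The plan does not rest its conclusions on that test. Its adjusted regression removes the baseline confounding and holds its level at about 5% in every scenario tried. What is left is missing detail in a short summary protocol: the form of a preliminary test, and an order of precedence that the wording already implies. A competent analyst would fill both sensibly.

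This rests on client entering the logistic model as a categorical term, which is the natural reading of controlling for client, and on the regression being reported as the answer. The percentages illustrate the mechanism under assumed inputs and do not estimate what would happen in this study.
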